8.2.6.1 Elevation of Liver Function Tests

In clinical studies with AAV-mediated gene transfer, a transient rise in liver transaminases and concurrent decline in transgene expression has been observed [Manno 2006; Nathwani 2011a; Nathwani 2014]. This has been hypothesized to be due to the activation of capsid-specific cytotoxic T lymphocytes (CTLs) and destruction of transduced liver cells [Mingozzi 2007]. However, in mice, T-cells activated against AAV capsid were not able to target and eliminate transduced hepatocytes [Wang 2007; Li C 2007; Li H 2007; Siders 2009] unless the wild-type AAV genome was present [Li C 2007].

The inability to reproduce the observed effects in animal models has made it difficult to assess the validity of the hypothesis or to develop strategies to overcome or minimize transaminase elevations. Despite a lack of clear resolution that activation of CTLs leads to a reduction in transgene expression from hepatocytes, appropriate precautions have been incorporated into this study. In addition to monitoring for capsid and FIX-specific T-cell activation, the use of oral steroids is allowed if a subject experiences elevations in liver transaminases.

If a subject experiences a >1.5 -fold increase in LFTs following treatment with DTX101, the investigator should consider the initiation of steroid treatment as outlined in [Section 8.2.6.2](#). The event should be recorded as an AE or SAE, as defined in [Section 9.1.2](#), on the appropriate pages of the eCRF if it is felt to be clinically significant in the medical and scientific judgment of the investigator.

8.2.6.2 Treatment for Potential Immune Hepatitis

In the absence of a specific etiology, steroid treatment for potential vector-induced immune hepatitis will be allowed if there is a >1.5 -fold increase from baseline in the subject's ALT that is considered related to treatment with DTX101 by the investigator. Within 24 hours of learning of the elevation, the site will repeat the test at their local laboratory and, if still elevated, will initiate steroid treatment.

The site is encouraged to consult with the medical monitor prior to initiating treatment. Based on available evidence, it is expected that vector-induced viral hepatitis will be self-limiting. Therefore, prednisone (or prednisolone) will be the sole medication used per the American Association for the Study of Liver Disease guidelines, with a slight modification:

- Week 1: prednisone 60 mg/day
- Week 2: prednisone 40 mg/day
- Week 3 and Week 4: prednisone 30 mg/day

Starting at Week 5, prednisone will be tapered by 5 mg/week until liver enzymes return to baseline levels. The use of prednisone will be recorded on the appropriate page of the eCRF.

8.3 Other Laboratory Parameters

8.3.1 Factor IX Inhibitor

Samples for FIX inhibitor will be collected at the time points specified in the Schedule of Events ([Table 15–1](#)) to monitor for an immune response to FIX. The Bethesda assay will be performed using a validated method. Details for the preparation and shipment of samples are included in the laboratory manual.

8.3.2 Neutralizing Antibodies to Adeno-Associated Virus rh10

Samples for neutralizing antibodies to AAVrh10 will be collected at the time points specified in the Schedule of Events ([Table 15–1](#)) to monitor for a humoral immune response to AAVrh10. The assay will be performed using a research method (enzyme-linked immunosorbent assay [ELISA]). Details for the preparation and shipment of samples are included in the laboratory manual.

8.3.3 Adeno-Associated Virus rh10 Binding Antibody IgG Assay

Samples for the AAVrh10 binding antibody IgG assay will be collected at the time points specified in the Schedule of Events ([Table 15–1](#)) to monitor for circulating anti-AAVrh10

antibodies. The assay will be performed using a research method (ELISA). Details for the preparation and shipment of samples are included in the laboratory manual.

8.3.4 Viral Shedding

Saliva, urine, and stool will be collected at the time points specified in the Schedules of Events ([Table 15–1](#) and [Table 15–2](#)) to monitor for the presence of shed virus. The presence of DTX101 will be determined by quantitative polymerase chain reaction (qPCR). Subjects will be given an appropriate container to collect a stool sample at home. Saliva and urine samples will be collected at the site. In the event the assay is positive, subjects will continue to provide weekly samples until the results are negative on 3 separate occasions for each sample matrix. Details for the preparation and shipment of samples are included in the laboratory manual.

8.3.5 Cell-Mediated Immune Response

The presence of T-cells specific for AAVrh10 and FIX will be determined by an enzyme-linked immunospot (ELISPOT) assay. Samples will be collected at the time points specified in the Schedule of Events ([Table 15–1](#)). Details for the preparation and shipment of samples are included in the laboratory manual.

8.4 Genotyping

8.4.1 Factor IX Genotyping

At baseline, subjects will be asked to provide a single whole-blood sample for FIX genotyping. The objective of this research is to provide a background understanding to the etiology of the subject's hemophilia B and to investigate any relationship between genetic factors and the subject's response to DTX101. The choice to provide this sample will be optional. If analyzed, the results will be reported separately. If not analyzed, the sample may be stored for future biological testing for a period of ≤ 15 years.

8.4.2 Human Leukocyte Antigen Genotyping

At baseline, subjects will be asked to provide an additional whole blood sample for human leukocyte antigen genotyping. The sample will only be analyzed if the result from the ELISPOT assay for cell-mediated immune response to AAVrh10 is ≥ 200 spot-forming units/ 1×10^6 peripheral blood mononuclear cells ([Section 8.3.5](#)). The objective of this research is to investigate any relationship between genetic factors and the subject's immune response to DTX101. The choice to provide this sample will be optional. If analyzed, the results will be reported separately. If not analyzed, the sample may be stored for future biological testing for a period of ≤ 15 years.

9 Safety Monitoring and Reporting

9.1 Adverse Events and Serious Adverse Events

Adverse events will be assessed from the time the subject signs the ICF until their exit from the study.

At every study visit, subjects will be asked a standard nonleading question to elicit any medically related changes in their well-being.

In addition to subject observations, AEs identified from any study data (eg, laboratory values, physical examination findings, ECG changes) or identified from review of other documents (eg, subject diaries) that are relevant to subject safety will be documented on the AE page in the eCRF.

9.1.1 Definitions

9.1.1.1 Adverse Events

The investigator is responsible for reporting all AEs that are observed or reported during the study, regardless of their relationship to study product or their clinical significance.

An AE is defined as any untoward medical occurrence in a subject enrolled into this study regardless of its causal relationship to study product. Subjects will be instructed to contact the investigator at any time after the subject signs the informed consent if any signs or symptoms develop.

A treatment-emergent adverse event (TEAE) is defined as any event not present before exposure to study product or any event already present that worsens in either intensity or frequency after exposure to study product.

9.1.1.2 Serious Adverse Events

An SAE is defined as any event that:

- Results in death
- Is immediately life threatening
- Requires inpatient hospitalization or prolongation of existing hospitalization
- Results in persistent or significant disability/incapacity, or
- Results in a congenital anomaly/birth defect.

Important medical events that may not result in death, be life threatening, or require hospitalization may be considered SAEs when, based upon appropriate medical judgment, they may jeopardize the subject or may require medical or surgical intervention to prevent one of the outcomes listed in this definition. Examples of such medical events include allergic bronchospasm requiring intensive treatment in an emergency room or at home, blood dyscrasias or convulsions that do not result in inpatient hospitalization, or the development of drug dependency or drug abuse.

9.1.2 Safety Reporting

9.1.2.1 Adverse Events

All AEs reported or observed during the study will be recorded on the AE page in the eCRF. Information to be collected includes drug treatment, dose, event term, time of onset, investigator-specified assessment of severity and relationship to study product, time of resolution of the event, seriousness, any required treatment or evaluations, and outcome. Adverse events resulting from concurrent illnesses, reactions to concurrent illnesses, reactions to concurrent medications, or progression of disease states must also be reported. All AEs will be followed to adequate resolution. The Medical Dictionary for Regulatory Activities (MedDRA) will be used to code all AEs.

Any medical condition that is present at the time that the subject is screened but does not deteriorate should not be reported as an AE. However, if the condition deteriorates at any time during the study, it should be recorded as an AE.

9.1.2.2 Serious Adverse Events

Any AE that meets SAE criteria ([Section 9.1.1.2](#)) must be reported to PPD Pharmacovigilance (PVG) immediately (ie, within 24 hours) after the time site personnel first learn about the event. The site should record all SAE information in the SAE eCRF and submit the report via the electronic data capture (EDC) system.

In the event of any fatal or life-threatening SAE, the investigator must immediately inform PPD PVG by telephone ([Table 9-1](#)) and report the SAE in the EDC system. If, for any reason, it is not possible to report the SAE in the EDC system (eg, the EDC system is unavailable), the site should record the SAE on the paper SAE Reporting Form and fax it to PPD PVG ([Table 9-1](#)). As soon as it is possible, any SAE reported via fax must be entered into the EDC system.

Table 9-1 PPD PVG Contact Information for SAE Reporting

Region	Contact Information
Rest of World	Safety hotline: [REDACTED]
	Safety fax^a: [REDACTED]
North America	Safety hotline: 1 [REDACTED]
	Safety fax^a: [REDACTED]

Abbreviations: PVG, pharmacovigilance; SAE, serious adverse event.

a. This is the preferred fax number for all regions. The toll free fax number for North America can be provided upon request.

9.1.2.2.1 Expedited Reporting

The sponsor is responsible for reporting suspected, unexpected, serious adverse reactions (SUSARs) involving the study product(s) to all regulatory authorities and participating investigators in accordance with ICH guidelines and/or local regulatory requirements, as applicable. It is the responsibility of the investigator or designee to promptly notify the local institutional review board (IRB)/independent ethics committee (IEC)/institutional biosafety committee (IBC) of all SUSARs involving risk to human subjects. Serious adverse reactions

will be assessed for expectedness using reference safety information specified in the Investigator's Brochure, as applicable.

9.1.3 Assessment of Severity/Toxicity

The severity/toxicity, or intensity, of an AE refers to the extent to which an AE affects the subject's daily activities. The intensity of the AE will be rated as Grade 1, 2, 3, 4, or 5 using the National Cancer Institute (NCI) Common Terminology Criteria for Adverse Events (CTCAE) v4.03 [[NCI CTCAE 2010](#)]. The CTCAE provides descriptive terminology that can be used to standardize AE reporting. A severity/toxicity grade is provided for each AE term that is grouped by the highest level of MedDRA classification [[NCI CTCAE 2010](#)]. Specific symptoms and medical conditions have a clinical description for each level of severity/toxicity. In the event that an AE occurs during the study that is not captured by the CTCAE, the AE should be graded according to the following general guidelines:

- Grade 1: Mild; asymptomatic or mild symptoms; clinical or diagnostic observations only; intervention not indicated.
- Grade 2: Moderate; minimal, local, or noninvasive intervention indicated; limiting age-appropriate instrumental ADL^a.
- Grade 3: Severe or medically significant but not immediately life-threatening; hospitalization or prolongation of hospitalization indicated; disabling; limiting self-care ADL^b.
- Grade 4: Life-threatening consequences; urgent intervention indicated.
- Grade 5: Death related to AE.

Abbreviation: ADL, activities of daily living; AE, adverse event.

- a. Instrumental ADL refers to preparing meals, shopping for groceries or clothes, using the telephone, managing money, etc.
- b. Self-care ADL refers to bathing, dressing and undressing, feeding self, using the toilet, taking medications, and not bedridden.

Changes in the severity/toxicity of an AE should be documented to allow an assessment of the duration of the event at each level of intensity to be performed. Adverse events characterized as intermittent do not require documentation of onset and duration of each episode.

9.1.4 Assessment of Causality

The investigator's assessment of an AE's relationship to study product is part of the documentation process, but it is not a factor in determining what is or is not reported in the study. If there is any doubt as to whether a clinical observation is an AE, the event should be reported.

The relationship or association of the study product in causing or contributing to the AE will be characterized using the following classification and criteria:

Unrelated: This relationship suggests that there is no association between the study product and the reported event.

Possible: This relationship suggests that treatment with the study product is causing or contributing to the adverse event (AE); ie, the event follows a reasonable temporal sequence from the time of the study product administration or follows a known response pattern to the study product, but could also be produced by other factors.

Probable: This relationship suggests that a reasonable temporal sequence of the event with the study product administration exists and, based upon the known pharmacological action of the study product, known or previously reported adverse reactions to the drug or class of drugs, or judgment based on the investigator's clinical experience, the association of the event with the study product seems likely. The event disappears or decreases on cessation or reduction of the dose of study product.

Definite: This relationship suggests that a definite causal relationship exists between the study product administration and the AE, and other conditions (concurrent illness, progression/expression of disease state, or concurrent medication reaction) do not appear to explain the event. The event reappears or worsens if the study product is re-administered.

9.1.5 Follow-Up of Subjects Reporting Adverse Events

All AEs must be reported in detail on the appropriate page in the eCRF and followed to satisfactory resolution, until the investigator deems the event to be chronic or not clinically significant, or until the subject is considered to be stable.

9.2 Procedures for Handling Special Situations

9.2.1 Pregnancy

The population under study is male; therefore, pregnancies will not be tracked.

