1.3 Study Rationale

1.3.1 Design Rationale

The design of this study is consistent with global regulatory guidelines for protocol design, including: subject selection, dose estimation, precautions applied between dosing cohorts, risk mitigation, and study stopping criteria.

Study 101HEMB01 is a Phase I/II, open-label, single-arm, multicenter, dose-finding safety study to determine the safety, tolerability, and efficacy of DTX101 in adult males with moderate/severe to severe hemophilia B. The primary objectives of the study are to determine the safety of single ascending IV doses of DTX101 and to identify the optimal biological dose (OBD) of DTX101 that either achieves or is the closest to achieving the target peak FIX activity of $\geq 20\%$ of normal.

Eligible subjects will receive a single IV infusion of DTX101. A minimum of 3 subjects will be enrolled per cohort. Subjects within a cohort will be dosed at a minimum of 1 week apart. Dose escalation will be conducted according to a model that uses both safety and efficacy data to predict the OBD ([Section 10.5.1](#)).

A Data Safety Monitoring Committee (DSMC) will meet after each dosing cohort to review subject safety (eg, AEs, physical examination findings, vital sign measurements, electrocardiogram [ECG] results, and clinical laboratory assessments including assessment of liver function) and provide their recommendation for progressing to the next dosing level ([Section 9.3](#)).

Subjects will be followed for 52 weeks after dosing. After completion of this study, subjects will be offered enrollment in an extension study to evaluate the long-term safety and effect of DTX101 on clinical outcome measures.

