3.1 Study Overview

Study 101HEMB01 is a Phase I/II, open-label, single-arm, multicenter, dose-finding safety study to determine the safety, tolerability, and efficacy of DTX101 in adults with moderate/severe to severe hemophilia B. The primary objectives of the study are to determine the safety of single ascending IV doses of DTX101 and to identify the OBD of DTX101 that either achieves or is the closest to achieving the target peak FIX activity of $\geq 20\%$ of normal.

Eligible subjects will receive a single IV infusion of DTX101. Subjects will be dosed sequentially in cohorts with a minimum of 3 subjects each. Dose escalation will be conducted according to a model that uses safety and efficacy data to predict the OBD ([Section 10.5.1](#)).

The following candidate doses (per kg of body weight) will be used to identify the OBD:

- **Dose 1:** 1.6×10^{12} GC/kg
- **Dose 2:** 3.0×10^{12} GC/kg
- **Dose 3:** 5.0×10^{12} GC/kg
- **Dose 4:** 1.0×10^{13} GC/kg

There will be a minimum of 7 days between dosing of each subject within a cohort and a minimum of 42 days between the dosing of the last subject in one dosing cohort and the first subject in the next dosing cohort. The recommendation to proceed to the next dose cohort will be made by the DSMC ([Section 9.3](#)) after evaluation of the safety data for all subjects in a dosing cohort after they have completed Week 6, as outlined in the DSMC charter. There will be no intra cohort dose escalations.

Study enrollment will be suspended if any of the safety stopping criteria are met ([Section 3.2.4](#)).

Subjects will be followed for 52 weeks after dosing. After completion of this study, subjects will be offered enrollment in an extension study to evaluate the long-term safety and effect of DTX101 on clinical outcome measures.

[figure not shown]

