4.1 Inclusion Criteria

Each subject must meet all of the following criteria at screening to be enrolled in this study:

1. Male ≥ 18 years of age.
2. Moderate/severe or severe hemophilia B (baseline FIX activity $\leq 2\%$ of normal or documented history of FIX activity $\leq 2\%$).
3. At least 3 bleeding episodes per year that require on-demand treatment with FIX OR are treated with a prophylactic regimen of FIX.
4. At least 100 days exposure history to FIX.
5. No documented history of inhibitors (neutralizing antibodies) to exogenous FIX.
6. No known allergic reaction to exogenous FIX or any component of DTX101.
7. Willing to stop prophylactic treatment with recombinant FIX at specified time points during the study.
8. Willing and able to provide written informed consent.
9. Willing and able to comply with study procedures and requirements.
10. Willing to use effective contraception at the time of administration of DTX101 and for 3 months following administration of DTX101. Appropriate contraceptive methods include a condom with spermicide. Abstinence, defined as sexual inactivity, is an acceptable form of birth control; however, appropriate contraception must be used if the subject becomes sexually active.

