6.2.4 Transmission of Infectious Agents

Recombinant AAV vectors are non-replicative and are not expected to pose a risk of transmission. However, all sexually active male subjects must use approved contraception from the time of dosing and for 3 months following. The study product and post-treatment study samples should be handled using standard universal precautions.

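### Partner pregnancies have no planned route of capture, although the protocol requires contraception for 3 months after dosing and lists birth defect as a seriousness criterion

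*Protocol*

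**What the plan says.** Protocol section 9.2.1 (Pregnancy) consists of one sentence: "The population under study is male; therefore, pregnancies will not be tracked". Section 1.3.1 describes the population as adult men, and inclusion criterion 1 in section 4.1 admits men only.

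Two other places treat conception after dosing as something to guard against:

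- **Section 4.1, inclusion criterion 10:** "Willing to use effective contraception at the time of administration of DTX101 and for 3 months following administration of DTX101".
- **Section 6.2.4:** "all sexually active male subjects must use approved contraception from the time of dosing and for 3 months following".

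Among the criteria that make an event serious, section 9.1.1.2 lists: "Results in a congenital anomaly/birth defect".

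Two further passages set the limits of safety collection. Section 9.1.1.1 states: "An AE is defined as any untoward medical occurrence in a subject enrolled into this study". Section 9.1 states: "Adverse events will be assessed from the time the subject signs the ICF until their exit from the study". Follow-up is 52 weeks after dosing (section 3.1).

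**The concern.** The reason given in 9.2.1 does not support the rule. It would be a sound reason for not testing subjects for pregnancy. It says nothing about partners, and in an all-male trial partners are the only people the rule can affect.

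The protocol takes a precaution against conception in the months after a gene-transfer vector is given, and then says it will not record what happens if the precaution fails. It also keeps a seriousness criterion that, for these subjects, could be met only through a partner's pregnancy.

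What is at stake is whether the sponsor would learn, through a planned route, of a partner pregnancy or an affected child after DTX101. Safety is the first primary objective and the product is given once, so information of this kind is worth having even though it would be rare.

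**Working it through.** The documents give no figure on this point, so the check is a comparison of passages, with one side calculation on timing.

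**1. Whom the rule concerns.** Only men are enrolled (sections 1.3.1 and 4.1). The word partner does not appear in 9.2.1, but no other pregnancy is possible in this population.

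**2. What is guarded against and what is recorded.**

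| Topic | Where | Content |
|---|---|---|
| Contraception | Protocol 4.1, 6.2.4 | At dosing and for 3 months after |
| Pregnancy | Protocol 9.2.1 | Not tracked |
| Birth defect | Protocol 9.1.1.2 | A seriousness criterion |
| Whose events count | Protocol 9.1.1.1, repeated in SAP 9.1 | Enrolled subjects only |
| How long events are assessed | Protocol 9.1 | From consent to study exit |

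**3. Whether another passage supplies a route.** The Schedules of Events (Protocol Tables 15–1 and 15–2, SAP Appendix B) have no pregnancy item. SAP section 9.1 has no pregnancy or offspring listing. Neither document describes a partner report, a partner consent or follow-up of an infant. The definition in 9.1.1.1 leaves a partner or child outside the adverse event system. Protocol sections 3.2.5 and 9.1.5 continue to monitor a subject's ongoing adverse events, but a partner's pregnancy is not one. An extension study is offered, but its procedures are not in these documents. The absence does not come from missing text, because 9.2.1 is present and explicit.

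**4. Timing of birth outcomes.** Assume 38 weeks from conception to delivery, range 36 to 40. This figure is not in the documents.

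- End of the contraception period: 3 months is 52/4 = 13 weeks, so about Week 13.
- Delivery of a pregnancy conceived at Week 13: 13 + 38 = Week 51 (range 13 + 36 = 49 to 13 + 40 = 53).
- Latest conception that delivers by Week 52: 52 − 38 = Week 14 (range 52 − 40 = 12 to 52 − 36 = 16).

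A pregnancy conceived within the contraception period would deliver at or before about the end of follow-up. Nearly all of those conceived later in the study would deliver after the subject has left. A rule that stopped at study exit would therefore miss most of the later outcomes, and could narrowly miss some conceived near Week 13.

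**The case against.** A reader might infer more than the documents support, in two ways.

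**That a birth defect cannot be detected.** This goes too far. Section 9.2.1 says pregnancies will not be tracked; it does not forbid a report. The seriousness criterion in 9.1.1.2 remains in force, and section 9.1.4 tells investigators to report when in doubt whether an observation is an adverse event. A spontaneous report could reach the sponsor. What is missing is a planned route.

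**That the incidence of one type of serious event is zero by construction, so the primary safety endpoint is biased.** The documents do not support this either. Protocol 9.1.1.1 and SAP 9.1 confine adverse events to enrolled subjects. A child's anomaly would lie outside the subject-level incidence whether or not pregnancies were tracked. The primary objective concerns safety in the treated adults, and 9.2.1 leaves that incidence intact.

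Three further arguments for leaving the text alone deserve weight:

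- The birth-defect line may be no more than part of a general list of seriousness criteria. A criterion that an all-male trial rarely or never meets is not in itself a contradiction. This stands, and the point does not depend on that line: the mismatch between 9.2.1 and the contraception requirement remains without it.
- Section 6.2.4 says the vectors are non-replicating and that transmission is not expected. Contraception is then a precaution, and a precaution does not logically commit a plan to outcome surveillance. This also stands. It makes the matter a design choice, but the choice should rest on a reason that addresses partners.
- The numbers are small and no analysis changes. This is correct, and it sets the weight of the point.

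**Conclusion.** The point holds as a gap in safety information. A partner pregnancy, or a child with a congenital anomaly, has no planned route of capture, and the male-only reason in 9.2.1 does not justify this beside a mandatory contraception period.

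Its size is small. With 12 to 18 subjects, few events, perhaps none, would be expected, and no rate could be estimated from them. Nothing changes in the sample size, the dose-finding model, the factor IX endpoint or the subject-level adverse event tables. The loss is in completeness: if an event did occur, the sponsor would depend on someone choosing to report it.

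The conclusion rests on the text alone. Only the timing calculation uses an outside assumption (36 to 40 weeks from conception to delivery). It bears on how the fix should be worded and not on whether the gap exists.

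**What to change.** Replace the sentence in Protocol 9.2.1 with a reporting rule:

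- A partner pregnancy conceived after DTX101 administration, at least through the protocol's own contraception period, is reported to the sponsor.
- With the partner's consent it is followed to outcome, even if that falls after the subject's study exit.
- A congenital anomaly is reported through the serious adverse event pathway as an offspring event. It is listed separately and not counted in the subject-level adverse event or serious adverse event incidence.

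The change has to be carried into the adjoining text so that sections 9.1, 9.1.1.1, 9.1.1.2 and 9.2.1 agree. As they stand, 9.1.1.1 excludes anyone who is not enrolled and 9.1 ends assessment at study exit; the new rule needs a stated exception to both. SAP 9.1 should add a separate listing for such events, if any occur. The sponsor should also state whether conceptions after the contraception period but within the 52 weeks are included, since the minimum wording leaves them without a route.

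The cost is one reporting form and one partner consent template, used only if an event occurs, plus short edits to the sections named. No visit, sample or analysis is added. This is a cheap improvement.
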